3.4. Enrollment Strategy

Study subjects will be recruited from the Institution/clinical site's subject database and/or utilizing Independent Ethics Committee (IEC) or Institutional Review Board (IRB) approved materials.

The overall goal is to enroll approximately 360 subjects and complete 330 that are evenly distributed between the Test Group and the Control Group (Table 1).

Table 1: Enrollment Strategy Overall

Strata	Number of subjects per Enrollment		Number of Subjects per Completion	
	Test	Control	Test	Control
Habitual Daily Disposable	~126 (~7 per site)	~126 (~7 per site)	~116 (~6 per site)	~116 (~6 per site)
Habitual Daily Wear Reusable	~54 (~3 per site)	~54 (~3 per site)	~49 (~3 per site)	~49 (~3 per site)
Total	~180 (~10 per site)	~180 (~10 per site)	~165 (~9 per site)	~165 (~9 per site)

Subjects will be enrolled from 18-20 clinical sites and approximately 20 subjects are targeted to be enrolled within each site. Habitual wearers of daily disposable lenses will be targeted in a 7:3 ratio over daily wear reusable wearers within each site.

Clinical Study Protocol

Johnson & Johnson Vision Care, Inc.

4. STUDY DESIGN AND RATIONALE

4.1. Description of Study Design

This study is a controlled, randomized, subject-masked, 2-arm parallel, 2-week dispensing, bilateral evaluation where the study lenses are worn for a minimum of 5 days per week and 6 hours per day. At study closure, participants will have no further access to the Test lenses.

The study begins with an initial visit (Visit 1). If a subject is found to meet all eligibility criteria, then they will be randomized and fit with either the Test or Control lenses in both eyes; otherwise, a subject will be deemed ineligible for this study. If the subject is dispensed study lenses at the initial visit, a follow-up visit will be conducted. The follow-up visit will occur approximately 2 weeks after the initial visit. Unscheduled visits may occur during the study.

4.2. Study Design Rationale

The purpose of this study is to evaluate the performance of a senofilcon A-based investigational lens in a 2-arm parallel design against a marketed product. In this parallel design, subjects are randomized to one of the two study arms and after randomization each participant will stay in their assigned treatment arm for the duration of the study. Randomization eliminates the selection bias and balances both the known and unknown confounding factors that may affect the study outcomes.

4.3. Enrollment Target and Study Duration

This study will have an enrollment target of 360 subjects, with a target of at least 330 to complete. The study will be conducted at 18-20 clinical sites, where the enrollment target for each site will be approximately 20 subjects. A subject will be considered enrolled upon signing of the informed consent form.

There will be 2 visits in total per subject; total study duration including the 4-week enrollment period is expected to be approximately 6 weeks. Subjects who are discontinued prior to the final evaluation may be replaced at the discretion of the study sponsor. The investigation will end at the time that the study data is hard locked.

Table 2: Duration of Study Visits

Visit	Description	≈ Duration
1	Informed consent, eligibility criteria, baseline data, trial fitting 1, dispense lenses. Study lenses to be worn 13-15 days to first follow-up visit.	2.0 hours
2	13-15 day follow-up for the study lens, subjective responses, VA, fitting characteristics, surface characteristics, physiology, Final Evaluation.	1.5 hours

Clinical Study Protocol

Johnson & Johnson Vision Care, Inc.

5. TEST ARTICLE ALLOCATION AND MASKING

5.1. Test Article Allocation

Use of the test articles will be randomized using a lens fitting schedule supplied by the study biostatistician. The clinical site will follow the lens fitting schedule provided and will complete enrollment according to the randomization list and will not pre-select or pre-assign subjects.

Randomly-permuted block randomization will be used to avoid bias in the assignment of subjects to treatment and to enhance the validity of statistical comparisons across treatment groups. A computer-generated randomization scheme will be used to randomly assign subjects to one of the two lens groups (Test or Control). The randomization will be stratified by site and type of habitual lens wear (daily disposable and daily wear reusable). The ratio of habitual wearers of daily disposable lenses to habitual wearers of daily wear reusable lenses is 7:3 within each study site (7 habitual wearers of daily disposable lenses versus 3 habitual wearers of daily wear reusable lenses). See Table 1. The random scheme will be generated using the PROC PLAN procedure from Statistical Analysis System (SAS) Software Version 9.4 or higher (SAS Institute, Cary, NC).⁵

Randomization will be performed at Visit 1. The following must have occurred prior to randomization:

- Informed consent must have been obtained.
- The subject must have met all eligibility criteria.
- The subject's screening and baseline information must have been collected.

When dispensing test articles, the following steps should be followed to maintain randomization codes:

1. Investigator or designee (documented on the Delegation Log) will consult the lens fitting schedule to obtain the test article assignment for that subject prior to dispensing.
2. Investigator or designee will record the subject's number on the appropriate line of the lens fitting schedule.
3. Investigator or designee will pull the appropriate test articles from the study supply. All test articles that are opened, whether dispensed (placed/fit on eye or dispensed outside the clinical site) or not, must be recorded on the Test Article Accountability Log in the "Dispensed" section.

5.2. Masking

This is a single-masked trial. Subjects will be unaware of the identity of the investigational product. The investigators may be aware of the study lenses based on a slight difference in lens color (the Test lenses will be slightly more turquoise in color than the Control lens). Investigators and clinical site personnel involved in the data collection will not be masked as to the identity of the investigational product.

Clinical Study Protocol

Johnson & Johnson Vision Care, Inc.

5.3. Procedures for Maintaining and Breaking the Masking

The identity of the study lenses will be masked to the subjects by over labeling the blister pack of the study lens. The label will contain the study number, lot number, sphere power, expiration date and the randomization codes.

The test articles mask shall not be broken unless information concerning the lens type is necessary for the urgent medical treatment of a subject. The Sponsor must be notified before the mask is broken.

Under normal circumstances, the mask should not be broken until all subjects have completed the study and the database is finalized. Otherwise, the mask should be broken only if specific emergency treatment/course of action would be dictated by knowing the treatment status of the subject. In such cases, the investigator may, in an emergency, contact the medical monitor. In the event the mask is broken, the sponsor must be informed as soon as possible. The date, time, and reason for the unmasking must be documented in the subject record. The investigator is also advised not to reveal the study treatment assignment to the clinical site or sponsor personnel.

Subjects who have had their treatment assignment unmasked are expected to return for all remaining scheduled evaluations. Subjects who are discontinued will be replaced.

6. STUDY INTERVENTION

6.1. Identity of Test Articles

The following contact lenses will be used in this study:

Table 3: Test Articles

	Control	Test
Manufacturer	Alcon	JJVC
Name	Dailies Total 1	TRP-200
Material	delefilcon A	senofilcon A
Packaging Form	Sterile blister pack	Sterile blister pack
Nominal Water Content (%)	33	38
Nominal Dk (edge corrected)	140	103
Inversion Indicator	No	123
Nominal Base Curve/Diameter @ 22°C (mm)	8.5 / 14.1	8.5 / 14.3
Nominal Center [contact] D (mm)	0.090	0.085
Nominal Powers (D)	-1.00 through -6.00 in 0.25 steps	-1.00 through -6.00 in 0.25 steps

Clinical Study Protocol

Johnson & Johnson Vision Care, Inc.

At least 1816 lenses per SKU per study lens will be made available based on the following factors: sample size, bilateral wear, daily replacement, 2-week duration, safety margin of 2X, and US distribution model for the range of lenses -1.00 through -6.00 DS.

6.2. Ancillary Supplies/Products

The following solutions will be used in this study. Note that RevitaLens will be used primarily to transport potential problematic lenses back to the Sponsor.

Table 4: Ancillary Supplies

Solution				
Solution Name/Description	Acuvue® RevitaLens Multipurpose Solution	Single use Eye-Cept® Rewetting Drops	LaciPure Saline Solution	ScleralFil Preservative Free Saline Solution
Manufacturer	Johnson & Johnson Vision	Optics Laboratory	Menicon	Bausch & Lomb
Preservative	Alexidine dihydrochloride 0.00016% and polyquaternium-1 0.0003%	None	None	None

[figure not shown]
Lens cases and fluorescein strips (either 0.6 mg or 1.0 mg) will be supplied for use as needed.

6.3. Administration of Test Articles

Test articles will be dispensed to subjects meeting all eligibility requirements, including any dispensing requirements set forth in this clinical protocol. Subjects will be dispensed an adequate supply of test articles to complete the study. Lost or damaged test articles may be replaced at the discretion of the investigator and/or the sponsor.

6.4. Packaging and Labeling

The Test articles will be packaged in blisters as the primary packaging. The Test article will be over-labeled to mask the identity of the lens. The Test articles will be in plastic bags as the secondary packaging form. The sample study label is shown below:

Clinical Study Protocol

Johnson & Johnson Vision Care, Inc.

6.5. Storage Conditions

Test articles will be maintained at ambient temperatures at the clinical site. Test articles must be kept under secure conditions.

6.6. Collection and Storage of Samples

No samples will be collected as part of the study procedures.

When possible, any lens or test article associated with an Adverse Event and/or a Product Quality Complaint must be retained and stored in a glass vial with moderate solution pending directions from the sponsor for potential return to JJVC.

6.7. Accountability of Test Articles

JJVC will provide the Investigator with sufficient quantities of study articles and supplies to complete the investigation. The Investigator is asked to retain all lens shipment documentation for the test article accountability records.

Test articles must be kept in a locked storage cabinet, accessible only to those assigned by the Investigator for dispensing. The Investigator may delegate this activity to authorized study site personnel listed on the Site Delegation Log. All test articles must be accounted. This includes:

1. What was dispensed for the subject for trial fitting, to wear out of the office, or issued for the subject to replace appropriately between visits.
2. What was returned to the Investigator unused, including expired or malfunctioning product.
3. The number and reason for unplanned replacements.

The Investigator will collect all unused test articles from the subjects at the end of the subject's participation. Subject returned unused test articles must be separated from the clinical study inventory of un-dispensed test articles and must be labeled with the subject number and date of return. Following final reconciliation of test articles by the monitor, the Investigator or monitor will return all unused test articles to JJVC.

If there is a discrepancy between the shipment documents and the contents, contact the study monitor immediately.

Reference [REDACTED] Site Instructions for Test Article Receipt and Test Article Accountability for additional information.

Clinical Study Protocol
Johnson & Johnson Vision Care, Inc.

7. STUDY EVALUATIONS

7.1. Time and Event Schedule

Table 5: Time and Events

Visit Information	Visit 1 Screening, Baseline, Treatment 1	Visit 2 2-week FU Treatment 1	Visit 2 Final Evaluation
Time Point		14 days after Visit 1 (+/- 1 day)	14 days after Visit 1 (+/- 1 day)
Estimated Visit Duration	2.0 hours	1.0 hours	0.5 hours
Statement of Informed Consent	x		
Demographics	x		
Medical History/Concomitant Medications	x	x	
Habitual Contact Lens Information	x		
Inclusion/Exclusion Criteria	x		
Study Questionnaires Baseline	x		
Entrance Visual Acuity	x	x	
Slit Lamp Biomicroscopy	x	x	x (if applicable)
Iris Color	x		
Subjective Spherocylindrical Refraction	x		x
Lens Selection	x		
Lens Insertion & Settling	x		
Visual Acuity and Over Refraction	x		
Lens Power Modification (if applicable)	x		
Subject Reported Ocular Symptoms	x	x	
Lens Fit Assessment	x	x	
Lens Wettability	x	x	
Surface characteristics		x	
Lens dispensing information and criteria	x		
Patient instructions	x		
Study Questionnaires FU		x	
Exit Acuity	x		x
Final Evaluation			x

Clinical Study Protocol
Johnson & Johnson Vision Care, Inc.

7.2. Detailed Study Procedures

VISIT 1

The subjects must enter the visit wearing their habitual contact lenses.

Visit 1: Screening			
Step	Procedure	Details	/
1.1	Statement of Informed Consent	
Each subject must read, understand, and sign the Statement of Informed Consent before being enrolled into the study. The Principal Investigator or his/her designee conducting the informed consent discussion must also sign the consent form.
 
Note: The subject must be provided a signed copy of this document.
	Work aid
1.2	Demographics	Record the subject's year of birth, age, gender, race and ethnicity.	/
1.3	Medical History and Concomitant Medications	Record the subject's medical history and concomitant medications.	/
1.4	Habitual Lenses	Record the subject's habitual lens type, parameters, lens care solution, wear modality and approximate prescription date.	/
1.5	Habitual Wear Time	Record the average wearing time and comfortable wearing time.	/
1.6	SCL Rx Confirmation	
The investigator confirms:
 
 1. The subject is wearing a SCL Rx that has been confirmed current (up-to-date) within the prior 6 months. 2. The subject has worn the up-to-date SCL Rx for at least 2 weeks. 	/
1.7	Eligibility after Screening	
All responses to Screening Inclusion Criteria questions must be answered "yes" and all responses to Exclusion Criteria must be answered "no" for the subject to be considered eligible.
 
If subject is deemed to be ineligible after screening, proceed to Final Evaluation and complete Subject Disposition. Refraction and Biomicroscopy forms do not need to be completed as part of Final Evaluation.
	/

Clinical Study Protocol
Johnson & Johnson Vision Care, Inc.

Visit 1: Baseline			
Step	Procedure	Details	Work aid
1.8	Baseline Questionnaire	
The subject will respond to the following Baseline Questionnaires based on their habitual lenses:
 
 1. CLUE baseline 2. GSI Background 3. Activity history 	
1.9	Entrance Visual Acuity	Record the distance Snellen visual acuity (OD, OS, and OU) to the nearest letter with their habitual contact lens correction in place. Subjects must read the smallest line until at least 50% of the letters are read incorrectly.	
1.10	Remove Habitual Lens	The subject's habitual lenses will be removed and stored in their own lens case. If they forgot to bring their lens case, one will be provided to them.	
1.11	Slit Lamp Biomicroscopy	
FDA Slit Lamp Classification Scale will be used to grade the findings and determine eligibility.
 
If any of these slit lamp findings are grade 3 or higher (FDA scale), the subject may not continue at this time, but may return up to one additional time to determine eligibility. If discontinued a final examination must be completed.
 
If the clearance of the fluorescein needs to be expedited, preservative-free rewetting drops or saline may be instilled.
	
1.12	Iris Color	The investigator will record the subject's iris color based on the scale provided.	Appendix E
1.13	Subjective Spherocylindrical Refraction	Complete subjective spherocylindrical refraction and record the resultant distance visual acuity (OD, OS, and OU) to the nearest letter.	

Clinical Study Protocol
Johnson & Johnson Vision Care, Inc.

Visit 1: Baseline			
Step	Procedure	Details	/
1.14	Eligibility after Baseline	
All responses to Inclusion Criteria questions must be answered “yes” and all responses to Exclusion Criteria questions must be answered “no” for the subject to be considered eligible.
 
If subject is deemed to be ineligible after baseline, proceed to Final Evaluation and complete Subject Disposition. Refraction and Biomicroscopy forms do not need to be completed as part of Final Evaluation.
	Work aid

Visit 1: Treatment 1 Lens Fitting			
Step	Procedure	Details	/
1.15	Lens Selection	
 • Assign the study lens based on the randomization scheme provided by the biostatistician. • Select the contact lens power based on the spherical equivalent from the subjective spherocylindrical refraction. • Record the test condition. 	Work aid Appendix F
1.16	Lens Insertion	
Patient instruction: the investigator will demonstrate / explain that the visibility tint for Test and Control lenses are there by design.
 
 • The Investigator or the subject inserts the study lenses. Record the time of lens insertion. • Check for lens damage under the slit lamp before proceeding with lens settling. • Replace damaged lenses if applicable. • Ensure the subject is given a Patient Instruction Guide. 	
1.17	Lens Settling	Allow the study lenses to settle for a minimum of 5 minutes.	

Clinical Study Protocol
Johnson & Johnson Vision Care, Inc.

Visit 1: Treatment 1 Lens Fitting			
Step	Procedure	Details	/ Work aid
1.18	Subjective Best Sphere Over Refraction	Perform subjective best sphere refraction over the study lenses with a phoropter (adopt the maximum plus to maximum visual acuity (MPMVA) approach and record the best corrected distance visual acuity to the nearest letter (OD and OS).	[REDACTED]
1.19	Lens Power Modification (if applicable)	Adjust the lens power if the subject's best sphere over-refraction is not plano. For each power modification, select the adjusted fitting lens power as appropriate and repeat steps 1.16 through 1.18. One power modification is allowed.	[REDACTED]
1.20	Subject Reported Ocular Symptoms	Subjects will respond to a verbal open-ended symptoms questionnaire.	[REDACTED]
1.21	Post-Fit Questionnaire	Subjects will respond to the MRD/GSI Post-Fit Questionnaire.	[REDACTED]
1.22	General Lens Fit Assessment	
Evaluate lens centration, movement on blink, and push-up test for each eye.
 
An unacceptable fit is deemed by one of the following criteria:
 
 • limbal exposure at primary gaze or with extreme eye movement. • edge lift. • excessive movement in primary and up gaze. • insufficient movement in all three of the following conditions: primary gaze, up gaze, and push-up test. 
Note: if lens fit is unacceptable for either eye, the subject will be discontinued from the study.
	[REDACTED]
1.23	White Light Lens Surface Wettability	Record the white light lens wettability of both lenses.	[REDACTED]
1.24	Visual Acuity	Record the distance visual acuity with the contact lenses (OD, OS, and OU) to the nearest letter. Smaller lines must be shown until the subject incorrectly identifies at least 50% of the letters.	[REDACTED]

Clinical Study Protocol
Johnson & Johnson Vision Care, Inc.

Visit 1: Treatment 1 Lens Fitting			
Step	Procedure	Details	/
1.25	Continuance	
For the subject to continue in the study, they must meet all three of the following criteria:
 
 • Visual acuity is 20/30 or better OD and OS. • The lens fit is acceptable OD and OS. • Investigator approval. 
If the Investigator does not approve the dispensing of the first study lens, then the study is terminated for that subject.
	Work aid
1.26	Dispense	
The lenses will be dispensed for 13-15 days
 
 1. The subjects should wear their lenses similar to the inclusion criteria: ≥ 6 hours per day, ≥ 5 days per week. 2. The lenses will be worn as daily wear daily disposable only. 3. All subjects will be provided a bottle of ACUVUE RevitaLens to return any problematic lenses to the investigational site. 4. Rewetting drops are permitted if needed. 5. A patient instruction booklet will be provided. 6. Has the subject been informed that the lenses contain a visibility tint by design? 
Note 1: Ensure that the subject has enough lenses to last them to their next scheduled visit with no extras. In the event a lens is lost or damaged, and the subject has run out of lenses, the subject will return to the investigator site for replacement.
 
Note 2: The subject's habitual contact lenses cannot be worn at any time during the study.
 
Note 3: Remind the subjects to bring back any unworn lenses to the next visit.
 
Note 4: Remind the subject to bring a habitual form of correction to next visit.
	Work aid
1.27	Schedule next visit	Schedule the follow-up visit to occur in 14 ± 1 days (counting the day of this visit as day 0, the subject may return on day 13 through 15).	Work aid

Clinical Study Protocol
Johnson & Johnson Vision Care, Inc.

VISIT 2

The follow-up will occur 13-15 days after Visit 1. The subjects must enter the visit wearing their study contact lenses.

Visit 2: Treatment 1 Follow-Up 1			
Step	Procedure	Details	/
2.1	Adverse Events and Concomitant Medications Review	Review any changes to the subject's medical history or concomitant medications from the previous study visit. Record any changes, and any adverse events.	
2.2	Wearing Time	Record the average wearing time and comfortable wearing time.	
2.3	Compliance	Confirm compliance with the prescribed wear schedule.	
2.4	Return unworn lenses	Collect any unworn study lenses from the subject.	
2.5	Subject Reported Ocular Symptoms	Subjects will respond to a verbal open-ended symptoms questionnaire.	
2.6	Follow-Up Questionnaire	Subjects will respond to the following questionnaires: 1. CLUE Follow-up 2. GSI Product Performance 3. Lens preference to habitual	
2.7	Visual Acuity	Record the distance Snellen visual acuity with the contact lenses (OD, OS, and OU) to the nearest letter. Subjects must read the smallest line until at least 50% of the letters are read incorrectly.	

Clinical Study Protocol
Johnson & Johnson Vision Care, Inc.

Visit 2: Treatment 1 Follow-Up 1			
Step	Procedure	Details	/ Work aid
2.8	Subjective Lens Fit Assessment	
Evaluate overall lens fit acceptance (acceptable or unacceptable) based on centration, movement and other fitting characteristics.
 
An unacceptable fit is deemed by one of the following criteria:
 
 • limbal exposure at primary gaze or with extreme eye movement. • edge lift. • excessive movement in primary and up gaze. • insufficient movement in all three of the following conditions: primary gaze, up gaze, and push-up test. 
Note: if lens fit is unacceptable subject will be discontinued from the study.
	
2.9	Wettability Characteristics	Record the white light lens wettability of both lenses.	
2.10	Surface Deposits	Record any front and back surface lens deposits.	
2.11	Lens Removal	Both lenses will be removed and discarded.	
2.12	Slit Lamp Biomicroscopy	
FDA Slit Lamp Classification Scale will be used to grade the findings. If no slit lamp finding is noted on the EDC form it is considered as a zero "0" grade for all observations listed.
 
Note: If the subject has Grade 3 or 4 slit lamp findings on the FDA scale, then they must be followed as an adverse event.
 
Adverse events must be reported to the JJVC monitors immediately.
 
After the slit lamp examination, at the discretion of the Investigator, rinse the subject's eyes thoroughly with rewetting drops or saline.
	

Clinical Study Protocol
Johnson & Johnson Vision Care, Inc.

FINAL EVALUATION

The final evaluation will ordinarily take place immediately following the last scheduled follow-up visit per the study protocol. It may also take place at any point the subject discontinues the study or is terminated from the study.

Final Evaluation		
Step	Procedure	Details
F.1	Final Exam Form	Indicate if the subject completed the study successfully. If subject discontinued from the study, indicate the reason.
F.2	Exit Refraction	Perform bare-eye subjective spherocylindrical refraction with a phoropter and record the best-corrected distance visual acuity (OD, OS and OU) to the nearest letter. Note: This step is not necessary if the subject was exited due to screen failure.
F.3	Exit Slit Lamp Biomicroscopy (for subjects that are discontinued early)	FDA Slit Lamp Classification Scale will be used to grade the findings. If no slit lamp finding is noted on the EDC form it is considered as a zero "0" grade for all observations listed. Note: If the subject has Grade 3 or 4 slit lamp findings on the FDA scale, then they must be followed as an adverse event. Adverse events must be reported to the JJVC monitors immediately. If the clearance of the fluorescein needs to be expedited, preservative-free rewetting drops or saline may be instilled. This step is not necessary if the subject was exited due to screen failure. Note: This step is not necessary if the subject was exited due to screen failure, or if biomicroscopy was performed as part of the final follow-up visit procedures (i.e., immediately prior to the final evaluation).

Clinical Study Protocol

Johnson & Johnson Vision Care, Inc.

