2.2. Endpoints

Primary Endpoint(s):

1. End of day comfort
 - Subjects will respond to the question, "Comfort at the End of the Day" [REDACTED].
 - Response set: Very Satisfied, Satisfied, Neither Satisfied nor Dissatisfied, Dissatisfied, and Very Dissatisfied.

Secondary Endpoint(s):

1. Digital device use
 - Subjects will respond to the question, "Reduction in the feeling of tired eyes from using a computer or other digital device" [REDACTED].
 - Response set: Not Applicable, Excellent, Very Good, Good, Fair, and Poor.
2. Comfort throughout the day
 - Subjects will respond to the question, "I could wear these contact lenses comfortably for as long as I wanted to" [REDACTED].
 - Response set: Strongly Disagree, Disagree, Neither Agree Nor Disagree, Agree, and Strongly Agree.
3. Comfortable vision while night driving
 - Subjects will respond to the question, "Ability to see comfortably while driving at night" [REDACTED].
 - Response set: Not Applicable, Excellent, Very Good, Good, Fair, and Poor.

Other Exploratory Endpoint(s):

Other exploratory endpoints including subjective questions regarding comfort, vision, handling, and preferences, such as:

Clinical Study Protocol

Johnson & Johnson Vision Care, Inc.

1. Clarity of distance vision
 - Subjects will respond to the question, “Clarity of distance vision (i.e. looking at things that are more than 5 feet away, such as street signs)” [REDACTED]
 - Response set: Not Applicable, Excellent, Very Good, Good, Fair, and Poor.
2. Vision clarity throughout the day
 - Subjects will respond to the question, “I was very satisfied by the clarity of my vision throughout the day” [REDACTED]
3. Didn't have to think about the lenses
 - Subjects will respond to the question, “I didn't have to think about my lenses until I was ready to take them out” [REDACTED]
 - Response set: Agree Strongly, Agree Somewhat, Neither Agree Nor Disagree, Disagree Somewhat, and Disagree Strongly.
4. Ability to see comfortably using digital devices
 - Subjects will respond to the question, “Ability to see comfortably while using a computer or other digital device” [REDACTED]
 - Response set: Not Applicable, Excellent, Very Good, Good, Fair, and Poor.
5. Tired eyes
 - Subjects will respond to the question, “My eyes felt tired” [REDACTED]
6. Eye fatigue
 - Subjects will respond to the question, “Eye fatigue” [REDACTED]
Response set: Always, Frequently, Occasionally, Rarely, Never, and Don't Know.
7. Vision at the end of the day

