2.3. Hypotheses

The primary hypothesis must be met for the objective of this study to be satisfied:

Clinical Study Protocol

Johnson & Johnson Vision Care, Inc.

Primary Hypothesis

1. After approximately two weeks of wear, the Test lens will have superior performance to the Control lens with respect to end of day comfort.

The primary hypothesis must be met in order to begin testing any secondary hypotheses.

Secondary Hypotheses

1. After approximately two weeks of wear, the Test lens will have superior performance to the Control lens with respect to digital device use.
2. After approximately two weeks of wear, the Test lens will have superior performance to the Control lens with respect to comfort throughout the day.
3. After approximately two weeks of wear, the Test lens will have superior performance to the Control lens with respect to comfortable vision while night driving.

Exploratory Hypotheses

There will be no exploratory hypotheses. All exploratory endpoints will be descriptively summarized.

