13.4.1. Reporting Adverse Events to Sponsor

Serious/Significant Adverse Events

The Investigator will inform the sponsor of all serious/significant adverse events occurring during the study period as soon as possible by e-mail or telephone, but no later than 24 hours following discovery of the event. The Investigator is obligated to pursue and obtain information requested by the Sponsor in addition to that information reported on the eCRF. All subjects experiencing a serious/significant adverse event must be followed up and all outcomes must be reported.

When medically necessary, the Investigator may break the randomization code to determine the identity of the treatment that the subject received. The Sponsor and study monitor should be notified prior to unmasking the test articles.

In the event of a serious/significant adverse event, the Investigator must:

Clinical Study Protocol

Johnson & Johnson Vision Care, Inc.

- Notify the Sponsor immediately.
- Obtain and maintain in the subject's records all pertinent medical information and medical judgment for colleagues who assisted in the treatment and follow-up of the subject.
- Provide the Sponsor with a complete case history which includes a statement as to whether the event was or was not related to the use of the test article.
- Notify the IEC/IRB as required by the IEC/IRB reporting procedure according to national regulations.

Unanticipated (Serious) Adverse Device Effect (UADE)

In the event of an Unanticipated (Serious) Adverse Device Effect (UADE), the Investigator will submit a report of the UADE to the Sponsor and IEC/IRB as soon as possible, but no later than 24 hours after the Investigator first learns of the effect. This report is in addition to the immediate notification mentioned above.

The Sponsor must conduct an evaluation of the UADE and must report the results of the evaluation to FDA, the IEC/IRB and participating Investigators within 10 working days after the Sponsor first receives notification of the effect.

Non-Serious Adverse Events

All non-serious adverse events, including non-serious adverse device effects, will be reported to the sponsor by the Investigator no later than 2 days from discovery.

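### At Visit 2, staff described as unmasked interview the subject about symptoms and record comfortable wearing time before the comfort ratings; putting the questionnaire first would close this possible route of influence

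*Combined protocol and SAP*

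**What the plan says.** **Order of Visit 2 (section 7.2).** The numbered steps are: adverse event and medication review (2.1); wearing time (2.2), worded "Record the average wearing time and comfortable wearing time"; compliance (2.3); return of unworn lenses (2.4); and symptoms (2.5), worded "Subjects will respond to a verbal open-ended symptoms questionnaire". Step 2.6 follows: "Subjects will respond to the following questionnaires: 1. CLUE Follow-up 2. GSI Product Performance 3. Lens preference to habitual". Acuity, fit, wettability, deposits, lens removal and slit lamp come later (2.7 to 2.12).

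**Masking (section 5.2).** The trial is single-masked. On site staff the section says: "Investigators and clinical site personnel involved in the data collection will not be masked as to the identity of the investigational product". One sentence earlier it is softer: "The investigators may be aware of the study lenses based on a slight difference in lens color". Section 5.3 sets rules for breaking the mask, and section 13.4.1 says that, when medically necessary, "the Investigator may break the randomization code to determine the identity of the treatment that the subject received".

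**Endpoints.** Section 2.2 names one primary endpoint, a single subject-rated item on end-of-day comfort, and three subject-rated secondary items. Section 14.2 places all four at the 2-week follow-up. Section 2.3 adds: "The primary hypothesis must be met in order to begin testing any secondary hypotheses".

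**The concern.** The trial seeks superiority over a marketed lens on a subjective rating given at one visit. Over-labelling hides the lens from the subject, but it does not control what staff say. The symptoms interview is the step directly before the ratings, it is spoken and open-ended, and the people who collect data are described as not masked. How far an answer is followed up could therefore vary with the lens.

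Step 2.2 also touches the endpoints in content. Comfortable wearing time is close to the second secondary item, which asks whether the lenses could be worn comfortably for as long as wanted.

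If such contact differed between arms, the ratings could move for a reason other than the lens. The section 14.5 model contains lens type, site and, when appropriate, subject characteristics. The only sensitivity analysis in section 14.9 is multiple imputation for missing data. Neither could separate a staff effect of this kind from a lens effect. Because the secondary hypotheses depend on the primary, all confirmatory claims rest on ratings collected in this way.

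**Working it through.** **1. What the text establishes about the contact before step 2.6**

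| Element | What the text supports |
|---|---|
| Symptoms, 2.5 | Verbal and open-ended; directly before the questionnaires |
| Comfortable wearing time, 2.2 | Recorded four steps before the questionnaires; how it is asked is not stated |
| Staff knowledge of the lens | Section 5.2 says data-collecting personnel are not masked, but also that investigators may be aware; 5.3 and 13.4.1 read as if the investigator does not know |
| Script or self-completion rule | Not in the visible text; Appendix A and the Appendix D instructions on symptoms and patient-reported outcomes are not shown |
| Time between 2.5 and 2.6 | Not stated |

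**2. Reproducing the plan's own figure.** Inputs from section 14.2: Test 68%, Control 48%, two-sided alpha 0.05, Pearson chi-square test. With p̄ the mean of the two rates, d = p1 − p2 and n per arm:

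- s0 = √[2·p̄(1 − p̄)/n]
- s1 = √{[p1(1 − p1) + p2(1 − p2)]/n}
- chance of declaring Test superior = 1 − Φ[(1.96·s0 − d)/s1]

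At n = 126: s0 = √(0.4872/126) = 0.0622 and s1 = √(0.4672/126) = 0.0609. Then (0.1219 − 0.20)/0.0609 = −1.283, so power is 90.0%, as in Table 10. At the planned 165 per arm, power for the primary endpoint is 96.1%.

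**3. Illustration of a differential shift.** Take no true lens difference (48% in both arms) and n = 165. Suppose reporting in the Test arm moves up by a net d. The documents give no value for d, so every value below is an assumption.

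- d = 0.03: s0 = 0.05505 and s1 = 0.05502; (0.1079 − 0.03)/0.05502 = 1.416; chance 7.8%.
- d = 0.05: s0 = 0.05505 and s1 = 0.05498; (0.1079 − 0.05)/0.05498 = 1.053; chance 14.6%.

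| Net shift favouring Test (points) | Chance of falsely declaring superiority |
|---|---|
| 0, including equal priming in both arms | 2.5% |
| 2 | 5.5% |
| 3 | 7.8% |
| 5 | 14.6% |
| 10 | 44.4% |

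In subjects, 3 points is 0.03 × 165 ≈ 5 in the Test arm, and 5 points is 0.05 × 165 ≈ 8. The figures use the chi-square test from the sample size section, not the mixed logistic model planned for the analysis.

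**4. Can the order be changed?** Subjects must arrive wearing the study lenses, and these stay in until step 2.11. Nothing in steps 2.1 to 2.5 is needed to complete step 2.6.

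**The case against.** A reader might infer more than the documents support, and the case against those stronger readings is good.

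- **That staff ask aloud about comfortable wearing time, minutes before the rating.** Only step 2.5 is called verbal. The COVID-19 appendix lists wearing time among topics for discussion with the subject, but that concerns remote visits. No timing within the visit is given.
- **That staff influence is uncontrolled.** Appendix D names controlled instructions for reported symptoms and for patient-reported outcomes. Their content is not shown. A fixed script or a self-completion rule may be there and cannot be called absent.
- **That everyone asking the questions knows the lens.** One sentence in section 5.2 says they are not masked, but the wording elsewhere pulls the other way.
- **That the primary comparison is biased.** The same open-ended step applies in both arms, and subjects are masked. Equal priming leaves the false-positive rate at about 2.5%. No text shows a difference by arm.

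Two further objections also stand. The illustration is not specific to step order: any net 5-point bias would give 14.6%. The assumed shifts are small beside the 20-point design difference and the historical rates in Table 9, which are (108 + 80)/227 = 82.8% for Test and (16 + 19)/72 = 48.6% for Control. The plan also already places the questionnaire before acuity, fit and slit lamp examination.

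The visible order remains. A spoken symptoms interview, at a visit run by staff described as not masked, precedes the only confirmatory ratings. A script would reduce its influence but would not change that order.

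**Conclusion.** The point holds as a possible risk and an optional improvement. The protocol places adverse event review, the recording of comfortable wearing time and a verbal symptoms interview before the ratings that carry the primary and all secondary endpoints. It describes the data-collecting staff as unmasked, and it plans no analysis that would reveal an effect of this contact.

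The documents do not show that the contact differs by arm, and harm depends on that. Under assumed net shifts of 3 or 5 points favouring Test, with 48% in both arms and 165 per arm, the chance of a false superiority claim would be about 8% or 15% instead of 2.5%. These figures show sensitivity; they do not estimate what will happen. The conclusion also assumes that the instructions not shown do not already have the subject complete the questionnaire alone before any discussion.

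**What to change.** Make the Follow-Up Questionnaire the first step of Visit 2, completed by the subject while still wearing the study lenses. Move present steps 2.1 to 2.5 to follow it, before lens removal. Content, staff, visits and sample size are unchanged; the cost is renumbering the Visit 2 table and updating site training.

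There is a small downside. Symptom and adverse event questioning would follow the questionnaire and could be slightly influenced by it, in the same way in both arms.

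The change closes only the Visit 2 route. At Visit 1, unmasked staff still select, assess and dispense the lenses and instruct the subject.

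Separately, reconcile the masking wording within section 5.2 and with sections 5.3 and 13.4.1, so that it is clear who is expected to know the lens.
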